The study also involves an increased utilization of CT and CBCT in order to quantify the difference in registration accuracy when using the mixed-reality method. Patients who receive a verification CT will receive 1-2 additional CT scans. During MixRT guided patient setup, patients will receive at least 0-10 additional CBCT scans (depends on modality). While it is routine for breast 3DCRT to employ planar kV imaging weekly as opposed to CBCT, it is not uncommon to utilize daily CBCT for difficult cases. Daily CBCT is also used for all cases where an IMRT approach is utilized. The dose from CBCT imaging is orders of magnitude less than the dose received during treatment, (approx. 1-2 mGy vs 45 Gy). According to the linear-no threshold model, there is non-zero risk of developing a radiation induced malignancy from any level of ionizing radiation. We believe the marginal increase in risk incurred through participation in this study, however, is low based on the limited amount of radiation delivered during CT and CBCT acquisition and the fact that these patients are already receiving high levels of ionizing radiation as part of their cancer treatment.

Only those Adverse Events related to the use of the HoloLens will be reported.

- **Identify potential financial risks study participants may incur:** None
- **Indicate any procedures, medications, tests, or therapies that study participants (or their insurer) will have to pay for. Are these considered standard therapies or are they specific to the research study?** None
- **Describe procedures to protect against or minimize potential discomforts and risks:** For individual cases, we will discontinue the use of the holographic alignment system if setup time is increased by more 30% during two consecutive sessions.

- **Discuss why the risks to subjects are reasonable in relation to the anticipated benefits and in relation to the importance of the knowledge that may reasonably be gained:** We believe the marginal increase in risk of developing a radiation induced malignancy incurred through participation in this study is low. The immediate benefit to the study participants is that the additional CT and CBCT may improve the accuracy of their setups for instances in which these images are acquired. The long-term benefit for patients outside the study cohort will be the knowledge gained about the clinical use of mixed-reality for patient setup. We believe this method can improve the patient setup and alignment process and will eventually make the process faster and with the use of less ionizing radiation.

10.) Possible Benefits:

- **Describe the potential benefits to subjects or to others that may be reasonably expected to result from the research:** Based on prior study utilizing anthropomorphic phantoms, we anticipate that our patient alignment system will ultimately reduce setup time and the number of X-ray images used for alignment. By reducing setup time, we increase patient comfort and minimize the risk of patient movement during treatment. By reducing the number of X-ray images used, we reduce the amount of ionizing radiation the patient receives.
- **If there is no potential for direct benefits, you must state this in the Informed Consent Form:** Due to the fact that CBCT will be utilized for all study fractions, patients may benefit from a more accurate setup if CBCT was not standard of care for their treatment approach.
- **Will the research study benefit future populations?** Yes, possibly.

11.) Conflict of Interest:

- **Describe any real or potential conflict of interest you or any other investigators may have with regard to this research project:** The principal investigator has filed a provisional patent application in coordination with UF Innovate related to concept of aligning a patient via hologram.
- **When deciding whether a conflict may exist, consider the following:**
 - **Do you, the University of Florida, or any of the sub-investigators hold a patent or license for any material, object, or process used in this project?** No
 - **Is a patent or license pending or under consideration or is there any intention to file a patent application at a later date?** Yes.
 - **Do you, the University of Florida, or any of the sub-investigators own stock in the company sponsoring the project?** No

- **Do you or any of the sub-investigators give presentations for or serve as a consultant to the sponsoring company on their behalf? No**

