- **Describe the inclusion and exclusion criteria for this project:** This study will target adult patients who are planning to undergo photon or proton radiation therapy at UFHPTI for treatment of the breast or chest wall. As this type of treatment is rare in men, the study will focus on female patients only.
- **Provide a thorough step-by-step description of what you intend to do throughout the course of the study in a logical and sequential format:**

Hologram creation

For all patients included in this study, we will create holograms based on the external body contour derived from their planning CT dataset. This contour is routinely segmented during treatment planning; thus, we will only need to access the existing contour located in the software system MimVista and export it to our software system. We will also access patient setup photos located in a clinical file system and export these to our application.

Mixed-reality guided patient setup

At UFHPTI, we treat breast/chest wall patients using various modalities and techniques. In all cases, patient setup begins with a 3-point alignment. The additional use of IGRT depends on modality, approach, and patient-specific variables. Most patients treated with 3D conformal photon therapy (3DCRT) receive only weekly IGRT, including kV orthogonal and MV portal imaging. The 3-point alignment, thus, represents the standard setup for the majority of treatment, both here and across the nation, as 3DCRT is the most common technique for breast RT. As such, one of our primary aims is to pilot the clinical implementation of MixRT with the goal of accuracy similar to or better than a traditional breast setup involving 3-point alignment (5mm tolerance).

We will recruit 12 patients scheduled to receive whole breast or chest wall RT using a supine, 3DCRT or IMRT approach. All patients will be consented for a study comparing the accuracy of MixRT with a traditional 3-point alignment as quantified using CBCT. To control for setup variation which typically decreases after the first few treatment fractions, we will stratify patients into two groups using an alternating method. In the first group, the therapists will position the patient using 3-point alignment during fractions 1-5 (5 total), then using MixRT for fractions 6-10 (note:

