16 fractions is a common course of breast RT). For the second group, we will reverse the order, using MixRT for fractions 1-5 and 3-point alignment for fractions 6-10. In this way, each patient will serve as their own control. In all cases, patient alignment will be verified using CBCT which will be registered to the simulation CT by the treatment therapists using the standard clinical workflow. The magnitude of the resulting shift will be recorded. If further adjustment is necessary, the number of repeated CBCTs will be recorded along with the shift magnitude. All registrations will be reviewed by a board-certified radiation oncologist (one of the co-investigators) who will qualitatively assess the accuracy of the setup while blinded to the setup method. The process for mixed-reality alignment is noted below:

1. Identify the patient and initialize their hologram by detecting a QR-coded cube attached to the treatment device.
2. Setup the patient according to their setup photos, related immobilization devices (typically only an inclined breast board), and 3-point alignment. Further match the patient to their hologram as viewed through the HoloLens 2 device.
3. Utilize IGRT to verify proper alignment per protocol or departmental standards.
4. Make corrections as needed based on IGRT.
5. Repeat steps 1-3 if necessary.

For patients receiving proton therapy, setup typically includes routine CBCT, the challenges of which were previously discussed for non-rigid alignment including prolonged setup time and increased imaging dose. The primary goal of this sub-aim is thus to show that MixRT can reduce setup time and the amount of imaging dose in cases requiring CBCT alignment. To evaluate this, we will recruit an additional 12 patients scheduled to receive RT using a supine, pencil-beam scanning approach. As with 3DCRT/IMRT approach, we will divide patients into two groups using an alternating method and alternate the setup approach between fractions 1-5 and 6-10, reversing the order between the two groups. Setup time will be tracked from the moment the patient lies on the treatment couch to when the final position is confirmed by the therapist prior to treatment. Patient alignment will be verified/quantified in a similar manner as noted above.

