- **Clearly state the nature of the experimental control (placebo, other treatment, historical) or the absence of a control:** Patients who receive verification CT, each patient will have their own control represented by the verification CT acquired without the use of holographic alignment. During the use of MixRT during patient setup, each patient will also have their own control represented by the sub-set of fractions where data is collected but holographic alignment is not employed.
- **Describe any randomization procedures:** Randomization is included during the use of MixRT guided patient setup where the patients are segmented into two groups. The order in which holographic alignment is introduced into the course of treatment is reversed for the two groups. The purpose is to control for setup variation which typically decreases after the first few fractions of treatment.
- **Describe completely all physical examinations, blood tests, x-rays, any special tests or procedures, surveys, questionnaires, and/or observations that will be used to obtain information about subjects:** No additional tests will be done that are outside the radiotherapy workflow. The study does include an increased utilization of specific aspects of the radiotherapy workflow, namely addition CT and CBCT acquisition.
- **Describe who will be responsible for obtaining the information and in what type of setting the information will be obtained:** Data will be collected during the course of radiotherapy treatment and during the acquisition of verification CT scans. Either the study investigators or trained radiation therapist will be responsible for collecting this data. The PI will serve as the primary data manager based on familiarity with the data.
- **Describe how these activities will answer the study questions:** The main question we seek to answer is whether mixed reality visualization is a feasible method for patient alignment in radiation therapy. To answer this question, we will collect relevant clinical data including registration error, registration time, and the amount of imaging used during the registration process. While we are not yet attaching power or a formal sample size structure to this data, we believe this data work together as our primary endpoints to answer the question of feasibility.

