- **Briefly outline the data analyses that are proposed and who will do the analysis:** Mean estimates and associated 95% confidence intervals will be attained for registration error and registration time for the mixed reality and standard of care methods and the paired difference of the two techniques. We will assess feasibility using a paired T-test. The hypothesis is that the mean paired differences across all measures of registration error and registration time are not significantly different than 3 mm and 5 minutes, respectively. The number of CBCTs collected as part of the registration process will be assessed subjectively since count data are not truly continuous. This analysis will be carried out by the study investigator and study statistician.
- **Describe your plan for conducting interim analysis. What stopping rules are in place?** N/A.

8.) Data Safety and Monitoring Plan:

- **Is there a Data Safety Monitoring Board (DSMB) or an oversight committee for this research project?** The UF Data Integrity & Safety Committee will provide oversight through annual monitoring.

- **Describe your plans for monitoring study conduct and subject safety:** The Principal Investigator will be responsible for monitoring.
- **Provide Information about the DSMB or committee including who is on the committee, how frequently will the committee meet, and when will you get information from the committee:** N/A

9.) Possible Discomforts and Risks:

- **Identify all discomforts and risks (physical, psychological, social, and/or economic) study participants may encounter, listing more common risks first and less common risks separately:** Based on prior study utilizing anthropomorphic phantoms, we anticipate that our patient alignment system will ultimately reduce setup time and the number of X-ray images used for alignment. We have yet to try this with patients, however, and there is a risk that it could marginally increase setup time, at least during the initial implementation.

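### The proton sub-aim is to show a shorter setup time, but the only named test compares the paired difference with 5 minutes, and the planned confidence interval that could show a reduction has no conclusion tied to it

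*Combined protocol and SAP*

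**What the plan says.** Section 6 (Research Plan, Mixed-reality guided patient setup) sets goals of different kinds for the two cohorts. For photon patients, MixRT is piloted "with the goal of accuracy similar to or better than a traditional breast setup". For the 12 proton patients the text reads: "The primary goal of this sub-aim is thus to show that MixRT can reduce setup time and the amount of imaging dose". Later in section 6, registration error, time and amount of imaging are taken together: "we believe this data work together as our primary endpoints to answer the question of feasibility".

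Section 7 (Statistical Analysis) makes no distinction between the cohorts. It plans estimation first: "Mean estimates and associated 95% confidence intervals will be attained for registration error and registration time", for each method "and the paired difference of the two techniques". It then says "We will assess feasibility using a paired T-test", and the hypothesis is that the mean paired differences "are not significantly different than 3 mm and 5 minutes, respectively". The direction of subtraction, the significance level and the sidedness are not given, nor is it said whether the cohorts are pooled. The number of CBCTs is to be judged subjectively. Sections 6 and 7 describe an underpowered pilot whose size was chosen for practical reasons.

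**The concern.** To show that MixRT reduces setup time, the analysis must show that the mean difference lies on the favourable side of zero. The named test takes 5 minutes as its reference. Even with the sign defined and 5 minutes read as a saving, it asks whether the saving equals 5 minutes, not whether there is one. The interval for the paired difference does bear on zero, but the plan does not say what would be concluded from it, whereas feasibility is explicitly attached to the t-test.

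Setup time is the only half of the proton goal with a formal analysis. If the section 7 hypothesis is used as the yardstick, a precise saving of 2 or 3 minutes, or of 8, would achieve what section 6 sets out to show and yet contradict the hypothesis. A report could then defend either conclusion from the same data. That matters because the protocol wants these results to establish viability and to frame larger comparative studies.

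**Working it through.** There is no power, SD or derived sample size in the documents to reproduce, so the check is of how the stated rule behaves.

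**Inputs**
- From section 6: n = 12 proton patients, each setup method used for five fractions per patient.
- From section 7: reference value 5 minutes; 95% interval for the paired difference.
- Assumed: fractions averaged to one difference per patient; cohorts not pooled; normal differences; two-sided 5% test, to match the 95% interval; SD of the paired difference 2, 3 or 4 minutes; section 7's registration time is section 6's setup time; 5 minutes is a saving.

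**Formulas.** Write d for the mean saving (standard minus MixRT; the opposite subtraction only changes signs).
- Interval: d ± t(0.975, 11) × SD/√12 = d ± 2.201 × SD/√12 = d ± 0.635 × SD.
- Reduction shown: the interval lies wholly on the side of zero that favours MixRT.
- Section 7 hypothesis contradicted: |d − 5| > 0.635 × SD.
- Each probability separately comes from the noncentral t distribution with 11 degrees of freedom and noncentrality (true saving)/(SD/√12) or (true saving − 5)/(SD/√12). The probability of both together comes from simulation.

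**One worked result.** Observed saving 2.5 minutes, SD 2. The standard error is 2/√12 = 0.577. The interval is 2.5 ± 1.27, or 1.23 to 3.77. Against zero, t = 2.5/0.577 = 4.33, p = 0.0012. Against 5, t = (2.5 − 5)/0.577 = −4.33, p = 0.0012. The saving is clear, and so is the departure from 5 minutes.

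**Long-run behaviour, n = 12**

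| True saving (min) | SD (min) | Interval shows a reduction | 5-minute saving rejected | Both |
|---|---|---|---|---|
| 2 | 2 | 0.883 | 0.997 | 0.88 |
| 2 | 3 | 0.558 | 0.883 | 0.45 |
| 2 | 4 | 0.353 | 0.658 | 0.13 |
| 3 | 2 | 0.997 | 0.883 | 0.88 |
| 3 | 3 | 0.883 | 0.558 | 0.45 |
| 3 | 4 | 0.658 | 0.353 | 0.13 |
| 5 | 2 | >0.99 | 0.050 | about 0.05 |
| 5 | 3 | 0.999 | 0.050 | about 0.05 |
| 5 | 4 | 0.975 | 0.050 | about 0.04 |
| 8 | 2 | >0.99 | 0.997 | >0.99 |
| 8 | 3 | >0.99 | 0.883 | 0.88 |
| 8 | 4 | >0.99 | 0.658 | 0.66 |

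The last column is the one that matters: the section 6 goal is met and the section 7 hypothesis is contradicted in the same trial. The rows for 2 and 3 minutes agree because both lie 0.5 minutes from 2.5, the midpoint of 0 and 5.

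As a check on the simulation, the joint probability cannot be below the sum of the two separate ones minus 1, nor above the smaller of them. For a 2-minute saving at SD 2 the limits are 0.883 + 0.997 − 1 = 0.880 and 0.883; at SD 3, 0.558 + 0.883 − 1 = 0.441 and 0.558; at SD 4, 0.353 + 0.658 − 1 = 0.011 and 0.353. The tabulated values fall inside.

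Pooling all 24 patients would sharpen the conflict. For a true 2.5-minute saving at SD 3, each separate probability rises from 0.748 (n = 12) to 0.974 (n = 24), so the joint probability is at least 0.974 + 0.974 − 1 = 0.948. A pooled difference would, however, no longer be the proton comparison.

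**The case against.** The strongest reply is that the comparison with zero is already there. A 95% interval that excludes zero is a two-sided 5% paired t-test against zero, and section 7 plans that interval. A reader might infer from the hypothesis sentence that the proton cohort cannot answer its own question. The documents do not support that: the information will be produced. What is missing is a sentence saying what it decides, and a statement that the proton cohort is analysed separately.

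A reader might also infer that a saving other than 5 minutes would be declared a failure of MixRT. No section says so. The t-test is tied to feasibility, three measures are said to bear on feasibility jointly, and there is no go/no-go rule. The conflict is therefore conditional on treating the hypothesis as the success criterion.

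Third, 5 minutes might be a tolerated slowdown, with the difference taken as MixRT minus standard. A real saving would then almost always reject 5 minutes, but from below, which favours MixRT. That high rejection rate should not be counted as damage here; it reflects the undefined sign and the use of non-significance as the hypothesis, which are separate matters. Even on this reading the test would show at most that MixRT is less than 5 minutes slower, not that it is faster.

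Fourth, the conflict is not universal. It is uncommon at SD 4 for small savings, and rare if the true saving is close to 5 minutes. Section 4 cites one surface-guidance study with a fall from 11 to 6 minutes, a saving of 11 − 6 = 5, but the protocol does not link that figure to its reference value.

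Finally, pilot status excuses low power. It does not excuse a hypothesis that differs from the stated goal.

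**Conclusion.** The mismatch holds. The proton goal is a reduction in setup time, the only named test does not address a reduction, and the planned interval that does has no conclusion attached. If the hypothesis is read as the success criterion, with 5 minutes as a saving, goal and hypothesis conflict in about 88/45/13% of trials at SD 2/3/4 for a true saving of 2 or 3 minutes, more than 99/88/66% for 8 minutes, and about 4 to 5% for 5 minutes.

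These sizes rest on 12 patient-level differences, unpooled cohorts and assumed SDs. The existence of the mismatch does not. It should be corrected before analysis, but it is a defect of the written rule, not of the data to be collected.

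**What to change.** In section 7, give the proton cohort its own setup-time criterion:

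- Analyse the proton cohort separately.
- Define the difference as MixRT/IGRT minus IGRT alone, so that a negative value is a saving.
- Conclude a reduction in setup time if the 95% interval already planned lies entirely below 0, and report the size of the saving with that interval.
- Make the 5-minute comparison descriptive for this cohort.
- Keep the photon accuracy criterion (at least comparable to 3-point alignment) as a separate statement.

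The cost is wording only: no new data, patients or analyses. The downside is that, with 12 patients and variable differences, a reduction may remain unproven. For a true 2-minute saving the interval would show it in about 35% of trials at SD 4. The report should then say that the result is inconclusive. The change does not cover the imaging half of the sub-aim, where the CBCT count would still be judged subjectively.

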A window period of 2 additional fractions is permissible for the collection of study data. This window period is provided to allow a patient to remain on study through her 12th fraction of treatment if the patient is not able to receive the study intervention during one to two of her first 10 fractions.

To summarize, we intend to enroll 12 patients receiving either 3DCRT or IMRT and 12 patients receiving proton therapy. Within each modality, patients will be randomized into two groups using an alternating method. The order in which MixRT will be utilized will be reversed between the groups. The measured data will include registration accuracy (6 DoF shifts), setup time, and number of CBCT's utilized. Registration accuracy will be quantified using the image registration module that is used as part of the IGRT process. Setup time will be quantified using a stopwatch.

The number of CBCT's will be quantified via counting the number that are used during the setup process. Patients receiving photon IMRT receive daily CBCT as part of the standard of care. Thus, this investigation would likely not introduce additional imaging dose for these patients. For proton therapy CBCT is used weekly, and for 3DCRT it is not routinely used. Thus, this investigation would represent a marginal increase in the utilization of CBCT for these patients, up to 10 extra CBCT's nominally.

Setup during Verification CT

Radiotherapy patients at UFHPTI often receive repeat CT scans (verification scans) at periodic timepoints during the course of treatment to assess for anthropomorphic changes that could have dosimetric effect. Reproducing the posture from the initial CT simulation is critically important yet difficult to achieve due to the lack of real-time feedback. For patients who receive a verification CT (likely all proton patients), we will implement holographic alignment during this process and assess its accuracy in comparison to CT acquisition without the aid of holographic alignment. The procedure will be as follows:

1. Identify enrolled patients scheduled to receive a verification CT scan.
2. Setup patient without the aid of holographic alignment (standard method).
3. Acquire verification CT scan.
4. Dismantle the setup.
5. Utilize holographic alignment to correct patient posture. This involves a therapist wearing the HoloLens 2 device and viewing the patient's reference hologram overlaid the patient. The therapist will manually adjust the patient to match the hologram.

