- **Describe how subjects protected health information will be accessed and by whom:** Data will be accessed and collected from the treatment planning system, RayStation, clinical database software, MimVista, and the radiation oncology information system, Mosaiq. These are all clinical systems used to facilitate patient treatment at UFHPTI. Only the investigators and research staff will screen or access patient medical records for the purpose of this study.
- **Describe how consent will be obtained, by whom, and in what setting, and how and where consent will be documented:** Patients will be consented during standard of care clinic visits by protocol/consent trained staff. Documentation of informed consent will be noted in the patient's chart in Mosaiq.
- **Describe the number of subjects that will be screened, and the number of evaluable subjects needed based on power analysis:** Up to 40 patients may enroll, but approximately 24 patients are needed in this pilot study. We recognize the study is underpowered, however, this is a pilot study where the purpose is to collect preliminary data to help establish viability of the method.
- **Describe completely all drugs, devices, or instruments that are being proposed:** This study involves no drugs. The specific device, HoloLens 2, will be worn by the therapists during patient setup. This device will display relevant information needed during the setup procedure including setup photos and the patient's hologram as registered to the radiotherapy device. Final positioning will be made according to IGRT which is standard of care.
- **Provide a clear and concise description of the treatment, intervention, or observation to be carried out in the study:** The intervention for the study is the use of the HoloLens v2 device to aid in patient alignment. As noted in the study

description above, this device utilizes mixed-reality to display a hologram of the patient as registered to the treatment machine. The patient will be matched to the hologram by a radiation therapist who is wearing the device. The patient will not wear the device. The device will not come into contact with the patient. The sensors on the device emit only non-ionizing signals such as IR.

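### Order of setup methods is assigned by predictable alternation but called randomization; bias follows only from steering on the expected fall in setup error or from unequal order groups

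*Combined protocol and SAP*

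**What the plan says.** Section 6 (Research Plan), under Mixed-reality guided patient setup, describes the allocation three times. For the photon cohort, "we will stratify patients into two groups using an alternating method". For the proton cohort, "we will divide patients into two groups using an alternating method and alternate the setup approach between fractions 1-5 and 6-10". The closing summary says that within each modality "patients will be randomized into two groups using an alternating method". Later in section 6, the item on randomization procedures states: "Randomization is included during the use of MixRT guided patient setup where the patients are segmented into two groups". None of these places mentions a random element, an allocation list, a person who holds it, or concealment from those who recruit.

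The design is a two-period crossover in which "each patient will serve as their own control". The order is reversed between groups to "control for setup variation which typically decreases after the first few treatment fractions". On numbers, "we intend to enroll 12 patients receiving either 3DCRT or IMRT and 12 patients receiving proton therapy", and the item on subject numbers adds: "Up to 40 patients may enroll, but approximately 24 patients are needed in this pilot study". Section 7 (Statistical Analysis) plans a paired t-test and mentions no period or order term. The only blinding is of the radiation oncologist who reviews the registrations qualitatively.

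**The concern.** The same procedure is called stratifying, dividing and randomizing, but it is alternation each time. Alternation contains no chance element. Once the first patient in a modality has an order, every later order follows from it.

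This matters because the protocol itself expects setup variation to fall after the early fractions. Reversing the order protects the comparison of methods only if the two order groups have the same expected fall and equal weight in the estimate. A concealed random sequence protects the first condition; alternation leaves it to the conduct of recruitment. The data are also meant to support larger comparative studies and eventual FDA clearance, so a label claiming a property the design lacks would be carried forward.

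**Working it through.** **Inputs from the documents.** 12 photon and 12 proton patients; alternation within modality; fractions 1-5 by one method and 6-10 by the other; a paired t-test with a 3 mm reference value for registration error. The size of the fall in setup error is not given, so every millimetre value below for the fall is an assumption. I also take the fall in setup variation to mean a fall in mean registration error.

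**1. The plan's own figure.** 12 + 12 = 24, which agrees with the stated number needed. The size was chosen for practicality, so there is no power calculation to reproduce. The allocation ratio is not stated; strict alternation gives 12 / 2 = 6 patients per order in each modality.

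**2. Predictability.** Expected share of orders guessed correctly by someone who knows all earlier ones and, for blocks, the block size:

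| Method | Share |
|---|---|
| Alternation, after the first patient | 100% |
| Permuted blocks of 4 | 71% |
| Permuted blocks of 6 | 68% |
| One balanced block of 12 | 64% |
| Simple randomization | 50% |

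Simple randomization gives an exact 6:6 split with probability 924 / 4096 = 22.6%.

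**3. Model.** Let d be a patient's error with MixRT minus error with the standard method, τ the true difference, and D the fall in error from fractions 1-5 to 6-10. Group A has the standard method first, group B has MixRT first.

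- Group A: mean of d = τ - D_A
- Group B: mean of d = τ + D_B
- Bias of the plain paired mean = (n_B·D_B - n_A·D_A) / (n_A + n_B)

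Negative values favour MixRT. With a common fall D at 6:6, the bias is (6D - 6D) / 12 = 0.

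**4. Steering at 6:6.** The bias is (D_B - D_A) / 2. Let δ be the difference in mean fall between two types of patient, and s the degree of steering of the larger-fall type to group A, so that D_A - D_B = s·δ and the bias is -s·δ / 2.

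| Steering | δ = 1 mm | δ = 2 mm |
|---|---|---|
| None | 0 | 0 |
| Quarter | -0.125 mm | -0.25 mm |
| Half | -0.25 mm | -0.5 mm |
| Full | -0.5 mm | -1.0 mm |

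As a second view, suppose that in each consecutive pair the patient with the larger expected fall is always put in group A. For normally distributed falls the bias is then -SD / √π, where SD is the between-patient standard deviation of the fall: -0.28, -0.56 and -0.85 mm for SD = 0.5, 1.0 and 1.5 mm. A simulation of 200,000 runs agreed, and steering half the pairs gave half the bias.

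**5. Unequal groups with a common fall, no steering.** The bias is D·(n_B - n_A) / 12.

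| n_A : n_B | D = 1 mm | D = 2 mm |
|---|---|---|
| 6:6 | 0 | 0 |
| 7:5 | -0.17 mm | -0.33 mm |
| 8:4 | -0.33 mm | -0.67 mm |

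The sign reverses if the MixRT-first group is the larger.

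**6. Effect of period adjustment.** Averaging the two order-group means gives [(τ - D) + (τ + D)] / 2 = τ for any split when the fall is common. If the falls differ, it gives τ + (D_B - D_A) / 2. Adjustment therefore removes the bias in step 5 but not that in step 4; only concealment protects against the latter.

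**The case against.** The strongest defence is the within-patient design. A patient who is simply harder to set up has larger errors with both methods, and this cancels. Bias from steering needs a difference in the fall, and recruitment takes place during pretreatment workup, before any fraction has been delivered, so nobody can observe the fall. Staff would have to predict it and reorder enrolment accordingly. Strict alternation also secures balance at enrolment, which a random list may not. Finally, the study is a declared underpowered pilot. With 12 patients the 95% confidence half-width is 2.201 / √12 = 0.635 times the standard deviation of the paired differences, or 0.95-1.9 mm for an assumed 1.5-3 mm, so quarter to half steering would sit inside the noise.

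Most of this stands and limits the point. It does not remove it. Difficulty of setup is partly foreseeable, since the protocol names pendulous breasts as a challenge, and the ceiling of 40 against about 24 needed leaves discretion over whom to approach. Balance at enrolment is not balance at analysis, because section 9 allows holographic alignment to be discontinued in individual cases.

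A reader might infer that recruiting staff know the next order and use it, or that any result from this crossover would be wrong. The documents support neither. They do not say who knows the last assignment, nothing in them indicates steering, and a wrong label does not by itself make the estimate wrong.

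**Conclusion.** The point holds as one of labelling and of a missing safeguard. The allocation is alternation, it is not randomized, and no concealment is described. That much rests on the text alone.

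The bias is conditional. Without steering and at 6:6, the expected bias is zero. An assumed 1-2 mm difference in falls gives 0.125-0.5 mm for quarter to half steering; 0.5-1.0 mm is an upper limit that needs full separation of patient types. An assumed common fall of 1 mm gives 0.17 mm at 7:5 and 0.33 mm at 8:4. These compare with the 3 mm reference value in section 7. For the proton cohort, where the primary goal concerns setup time and imaging dose, the same algebra applies in minutes, but the documents give no basis for a figure. The verification-CT comparison uses a fixed order and is not touched by this point.

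The change is worth making because it is cheap, not because bias has been shown.

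**What to change.** - **Section 6, Mixed-reality guided patient setup (photon, proton and summary paragraphs).** Replace alternation with a computer-generated sequence in permuted blocks of varying size. Keep the existing separation by modality. The study statistician holds the list and releases each order only after consent is documented.
- **Section 6, item on randomization procedures.** Describe how the sequence is generated, who holds it and when it is released.
- **Section 7, data analyses.** Estimate the paired difference with adjustment for period, as the average of the two order-group means. This is needed with the new sequence because exact balance is no longer assured, and it is also useful if alternation is kept.
- **If alternation has already been used.** Remove the words randomized and randomization, describe the allocation as alternation, and report it as a limitation.

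The cost is a short list to prepare and edits to these paragraphs. Exact 6:6 balance may be off by one or two if enrolment stops within a block. The period term costs one degree of freedom, from 12 - 1 = 11 to 12 - 2 = 10 in each modality. Blocks remain partly guessable to someone who knows the earlier orders and the block size, so the block sizes should not be disclosed to recruiting staff. The sample size does not change.
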